9 CHANGES IN THE CONDUCT OF THE STUDY OR PLANNED ANALYSIS

9.1 Changes in the Conduct of the Study

No changes in the conduct of the study are foreseen.

9.2 Changes in the Planned Analysis

We will check for violation of assumptions of the two-sample t-test instead of using a two-sample equal-variance t-test routinely. As appropriate, we will (log)transform the scores in case of non-normality or perform a test for unequal variances in case of unequal variances between

Document ID:	<As applicable, per local requirements>	Document title:		Classification:	For internal use
		Statistical Analysis Plan			
Modified:	11MAY2023			Author:	
Version:	3.0	Template ID:	ClinicalStudyTemplate0025	Approver:	
Status:	Final	Template Version Date:	02MAR2018	Page:	39 of 52

Statistical Analysis Plan

groups. For AKI and Procedural success, we will perform a Chi-square test or Fisher exact test as appropriate. We removed the cluster analysis from the study.

The protocol states that we will define subgroups of simple, intermediate and complex PCI, in which the patients' SYNTAX score for the vessel(s) treated with PCI will be used as an index for complexity. We will define 3 subgroups based in the patients' SYNTAX score divided into tertiles and label them as Complexity 1st Tertile, Complexity 2nd Tertile and Complexity 3rd Tertile instead of using the labels Simple, Intermediate and Complex PCI.

In the protocol is stated for that for the primary, secondary and exploratory endpoints all subjects will be included in the analysis. In the SAP this is specified as 'All subjects in the FAP population will be included in this analysis. The analysis will be repeated for the PP population.'

11 TABLES

STUDY PATIENTS		
Disposition of patients		
Table 1	Enrolment by Site	ENROLLED
Table 2	Randomized Population by Site	RAND
Table 3	Stratification Factors by Randomized Treatment	RAND
Table 4	Screen Failures	SCREENED
Table 5	Disposition by Randomized Treatment	RAND
Table 6	Reason for Non-completion by Randomized Treatment	RAND
Table 7	Analysis Populations	SCREENED
Table 8	Analysis Populations by Randomized Treatment	RAND
BASELINE EVALUATION		
Demographics and other baseline characteristics		
Table 9-10	Demographics	RAND, FAP
Table 11-12	Medical History	SAF, FAP
Table 13/15	Medication Used	SAF, FAP
Table 14/16	Iodine Contrast Administration	SAF, FAP
PCI PROCEDURE		
Table 17/19	PCI Procedure	SAF, FAP
Table 18/20	Complications during Procedure	SAF, FAP
Table 21/23	SYNTAX score per vessel	SAF, FAP
Table 22/24	Total SYNTAX score	SAF, FAP
EFFICACY EVALUATION		
Analysis of efficacy		
Table 25/26	Primary Outcome - Total Undiluted Iodinated Contrast Volume (ml) - Descriptive Statistics	FAP, PP
Table 27/28	Secondary and Exploratory Outcomes - Descriptive Statistics	FAP, PP
Table 29/30	Primary Efficacy Analysis on Log-transformed Total Undiluted Iodinated Contrast Volume (ml)	FAP, PP
Table 31/32	Secondary Efficacy Analysis	FAP, PP
Table 33/34	Exploratory Efficacy Analysis	FAP, PP
Table 35/36	Exploratory Outcomes	FAP, PP

Document ID:	<As applicable, per local requirements>	Document title:	Classification:	For internal use
Modified:	11MAY2023	Statistical Analysis Plan		
Version:	3.0	Template ID:	ClinicalStudyTemplate0025	Approver:
Status:	Final	Template Version Date:	02MAR2018	Page: 43 of 52

Statistical Analysis Plan

Table 37/38	Exploratory Efficacy : Total Iodinated Contrast Volume by Number of vessels treated	FAP, PP
Table 39/40	Exploratory Efficacy : Total Iodinated Contrast Volume by Complexity of PCI procedure	FAP, PP
Table 41/42	Total Iodinated Contrast Volume by Roadmap Quality	FAP, PP
Table 43/44	Exploratory Efficacy : Variability of Total iodinated Contrast Volume by Randomized Treatment	FAP, PP

SAFETY**Vital Signs**

Table 45	Vital Signs	SAF
-----------------	-------------	-----

Clinical laboratory evaluation

Table 46/47	Serum Creatinine	SAF, FAP
Table 48/40	Acute Kidney Injury	SAF, FAP

Major Adverse Cardiovascular and Cerebral Events

Table 50/51	In-Hospital MACCE	SAF, FAP

STUDY DEVIATIONS

Table 52	Major Protocol Deviations	FAP
Table 53	Study Deviations	FAP

Document ID:	<As applicable, per local requirements>	Document title:	Classification:	For internal use
Modified:	11MAY2023	Statistical Analysis Plan		
Version:	3.0	Template ID:	ClinicalStudyTemplate0025	Approver:
Status:	Final	Template Version Date:	02MAR2018	Page: 44 of 52

Statistical Analysis Plan

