6.1. General

This is a multi-center, prospective, unblinded, stratified 1:1 randomized controlled trial to assess whether using Dynamic Coronary Roadmap reduces the total iodinated contrast volume related to PCI compared to the control group without Dynamic Coronary Roadmap. In the randomization process all subjects within each type of PCI (ad hoc or elective) will be stratified according to the number of vessels to be treated via PCI, i.e., 1, 2, or 3 or more vessel PCI.

A prospective multi-center study has been chosen to observe standard of care with the study device, see Figure 3 for the DCR4Contrast trial flow.

[figure not shown]

Figure 3 Clinical workflow of the DCR4Contrast trial following standard of care for PCI (ad hoc and elective)

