4.4.2 Randomization

The randomization will be performed via the Electronic Data Capture (EDC) system hosting the electronic Case Report Form.

In order to ensure balance of the treatment groups across subgroups, we stratified the randomization by site and within site by type of PCI (ad hoc or elective) and the number of vessels to be treated via PCI, i.e., 1, 2, or 3 or more vessel PCI. Within the subgroups we will perform a permuted block design. We will use a block size of 4 patients per block. There will be an equal allocation to the PCI procedure with DCR and the PCI procedure without the use of DCR (1:1 randomization).

In case of elective PCI, randomization will be done before the procedure and in case of ad hoc PCI randomization will be done upon decision to go for PCI right after diagnostics, so when the patient on the table still.

In enrolled subjects the investigator pre procedurally deemed no usage of OCT and/or the rotational or orbital atherectomy is required. During the PCI procedure usage of OCT and/or rotational or orbital atherectomy is left to the investigator's discretion.

In the case OCT and/or rotational or orbital atherectomy is used in enrolled subjects, these subjects will be replaced. When the decision is made to replace a subject this subject will not count for the required total number of subjects total, but will still be part of the Safety population. A new subject will be randomized to either of the arms.

Document ID:	<As applicable, per local requirements>	Document title:		Classification:	For internal use
		Statistical Analysis Plan			
Modified:	11MAY2023	Template ID:	ClinicalStudyTemplate0025	Author:	
Version:	3.0	Template Version Date:	02MAR2018	Approver:	
Status:	Final			Page:	11 of 52

Statistical Analysis Plan

Thus, the following subjects will be replaced:

- Subjects undergoing PCI supported by OCT will be replaced.
- Subjects undergoing PCI supported by rotational or orbital atherectomy will be replaced.

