8.10 Procedure characteristics

Type of PCI (ad hoc PCI or elective (scheduled) PCI) and number of vessels treated by PCI (1 vessel PCI, 2 vessel PCI, 3 or more vessel PCI) will be summarized by treatment group for the FAP and the SAF. In addition, the SYNTAX score will be presented for the vessel(s) treated with PCI as an index for anatomical complexity. The SYNTAX score will be summarized in categories and as a continuous variable.

Also pre-procedural hydration (Y/N) and discontinuation of any renal drugs (e.g. ACE inhibitors) (Y/N) will be summarized in this table.

The access method (Transfemoral, Transradial, Other) and whether Femoral angiography was performed (if Transfemoral=Yes) and the timing of the Femoral angiography will be presented as categorical variables. Contrast usage details such as contrast injector (ml) at skin incision, generic name of iodine contrast used and contrast injector speed (ml/s) will be summarized.

The following information measured at the end of the PCI procedure will be summarized by treatment group for the FAP and the SAF:

- Procedure time (min)
- Total procedural contrast volume read-out of contrast injector (ml)
- Total number of stent(s) placed
- Total size of stent(s) placed (mm)
- Total number of balloon inflations
- Physiology assessment (instantaneous wave-Free Ratio (iFR) or Fractional Flow Reserve (FFR)) (Y/N)
- IVUS (Y/N)
- Any complication(s) during procedure (Y/N)
- Procedural success (Y/N)
- Total fluoroscopy time (mm)
- Total Air Kerma (mGy)

Document ID:	<As applicable, per local requirements>	Document title:		Classification:	For internal use
Modified:	11MAY2023	Statistical Analysis Plan		Author:	
Version:	3.0	Template ID:	ClinicalStudyTemplate0025	Approver:	
Status:	Final	Template Version Date:	02MAR2018	Page:	27 of 52

Statistical Analysis Plan

- Total Dose Area Product (DAP; Gy*cm²)
- Total Exposure DAP (Gy*cm²)
- Total Fluoroscopy DAP (Gy*cm²)
- Total number of exposure series (runs)
- Total number of exposure images
- Total number of contrast enhanced angiograms
- Total number of Stent Boost (runs)
- Post-procedural hydration (Y/N)
- Dynamic Coronary Roadmap used (Y/N)
- Overall quality and accuracy of roadmap (very good/ good/ fair/ poor/ very poor)

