8.11.3 Exploratory Efficacy Analysis

8.11.3.1 Contrast Volume per Vessel PCI

The average undiluted iodinated contrast volume (in ml) used per vessel PCI (from first positioning the interventional guiding catheter in stable coronary position till end of PCI procedure) by treatment group. For multi vessel PCI the iodinated contrast volume used per vessel PCI will be determined based on the total PCI contrast volume (from first positioning the interventional guiding catheter in stable coronary position till end of PCI procedure) divided by the number of vessels actually treated by PCI.

Descriptive summaries of the total undiluted iodinated contrast volume divided by the actual number of vessels treated by PCI will be presented by treatment group for the FAP and the PP population and will include the number of subjects with non-missing data (n), mean with 95% confidence interval, standard deviation (SD), median, interquartile range (IQR) and minimum and maximum values.

The endpoint will be evaluated using a one-sided two-sample t-test. We will test for assumptions, e.g. normality and equal variances. Normality will be checked using histograms and Q-Q plots. If there are strong indications of non-normality, the data will be (log)transformed, and the back transformed results will be presented. Levene's test for equality of variances will be applied. When the p-value of this test is greater than 0.05, then we assume the variances are equal and we will use the arithmetic mean of the variances in calculating the standard error. When the p-value is less than or equal to 0.05, then we assume

Document ID:	<As applicable, per local requirements>	Document title:		Classification:	For internal use
		Statistical Analysis Plan			
Modified:	11MAY2023	Template ID:	ClinicalStudyTemplate0025	Author:	
Version:	3.0	Template Version Date:	02MAR2018	Approver:	
Status:	Final			Page:	31 of 52

Statistical Analysis Plan

the variances are unequal and then we will calculate the standard error from the weighted average of the two variances.

The results of the t-test will be displayed as estimates of the between treatment group difference (with 95% confidence intervals) and the (one-sided) p-value for the between treatment group difference. When the p-value is lower than the significance level of 2.5% (alpha) we will reject the null hypothesis.

All subjects in the FAP population will be included in this analysis. The analysis will be repeated for the PP population.

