8.11.3.2 Contrast Volume per Stratification Group (1, 2, 3 or more vessel PCI)

The total undiluted iodinated contrast volume (in ml) used per PCI (from first positioning the interventional guiding catheter in stable coronary position till end of PCI procedure) in each stratification group, i.e., 1 vessel PCI, 2 vessel PCI and 3 or more vessel PCI.

Descriptive summaries of the total undiluted iodinated contrast volume will be presented by treatment group and by stratification group (1 vessel PCI, 2 vessel PCI and 3 or more vessel PCI) for the FAP and the PP population and will include the number of subjects with non-missing data (n), mean with 95% confidence interval, standard deviation (SD), median, interquartile range (IQR) and minimum and maximum values.

The endpoint will be evaluated per subgroup (1 vessel PCI, 2 vessel PCI and 3 or more vessel PCI) using a one-sided two-sample t-test. We will test for assumptions, e.g. normality and equal variances. Normality will be checked using histograms and Q-Q plots. If there are strong indications of non-normality, the data will be (log)transformed, and the back transformed results will be presented. Levene's test for equality of variances will be applied. When the p-value of this test is greater than 0.05, then we assume the variances are equal and we will use the arithmetic mean of the variances in calculating the standard error. When the p-value is less than or equal to 0.05, then we assume the variances are unequal and then we will calculate the standard error from the weighted average of the two variances.

The results of the t-test will be displayed as estimates of the between treatment group difference (with 95% confidence intervals) and the (one-sided) p-value for the between treatment group difference. When the p-value is lower than the significance level of 2.5% (alpha) we will reject the null hypothesis.

All subjects in the FAP population will be included in this analysis. The analysis will be repeated for the PP population.

Document ID:	<As applicable, per local requirements>	Document title:		Classification:	For internal use
		Statistical Analysis Plan			
Modified:	11MAY2023			Author:	
Version:	3.0	Template ID:	ClinicalStudyTemplate0025	Approver:	
Status:	Final	Template Version Date:	02MAR2018	Page:	32 of 52

Statistical Analysis Plan

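### Contrast volume by vessel number is specified by randomisation stratum in the text, but its only matching table is titled by vessels treated, a count fixed after allocation

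*SAP*

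**What the plan says.** **The stratum is a planned count.** Protocol 6.1 has patients "stratified according to the number of vessels to be treated via PCI, i.e., 1, 2, or 3 or more vessel PCI", and SAP 4.4.2 uses "the number of vessels to be treated via PCI, i.e., 1, 2, or 3 or more vessel PCI" as a factor within site. On timing, SAP 4.4.2 states: "In case of elective PCI, randomization will be done before the procedure". Ad hoc patients are randomised after the diagnostic angiogram, once PCI is decided on.

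**The analysis text follows the stratum.** Protocol 7.8.2 and SAP 8.11.3.2 are both headed as analyses per stratification group. The SAP reports volume "in each stratification group, i.e., 1 vessel PCI, 2 vessel PCI and 3 or more vessel PCI" and gives each group its own one-sided t-test with a 2.5% rejection rule.

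**The table list does not.** The SAP section 11 output for this analysis, Table 37/38, is "Total Iodinated Contrast Volume by Number of vessels treated". No listed table shows contrast volume by stratum. The strata appear only in Table 3, "Stratification Factors by Randomized Treatment".

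**The SAP uses both counts.** Section 8.11.3.1 takes total volume "divided by the number of vessels actually treated by PCI". Section 8.10 summarises "number of vessels treated by PCI (1 vessel PCI, 2 vessel PCI, 3 or more vessel PCI") as a procedure characteristic, with the same three labels that serve for the strata. Section 8.13 uses those labels without saying which count is meant. Section 9.2 lists departures from the protocol and does not include a change from stratum to vessels treated.

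**The concern.** The number of vessels treated is known only after allocation. The operator knows the arm, and the procedure steps in Protocol 6.5 allow PCI in a further vessel during the same session. The count could therefore depend on the device, or on how the case went, and patients whose treated count departs from the plan need not be a random subset.

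A comparison within a planned stratum compares groups formed by randomisation. A comparison among patients with one vessel treated does not: if different kinds or proportions of patients leave or join that group in the two arms, the difference mixes any device effect with a difference in case mix. Because the same labels serve both counts and no rule covers patients in whom they differ, a programmer could build Table 37/38 either way and believe the SAP had been followed. At stake is how the vessel-group estimates and their p-values can be read.

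**Working it through.** **1. The texts side by side**

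| Place | Grouping named | Fixed before allocation? |
|---|---|---|
| Protocol 6.1, SAP 4.4.2 | vessels planned for PCI | yes |
| Protocol 7.8.2, SAP 8.11.3.2 | stratification group | yes |
| SAP 8.13 | 1, 2, 3 or more; count not stated | unclear |
| SAP 8.10 | vessels treated | no |
| SAP Table 3 | stratification factors | yes |
| SAP Table 37/38 | vessels treated | no |
| SAP 9.2 | no change recorded | n/a |

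The analysis and its output name different variables. No stated figure depends on this, so there is no figure of the plan to reproduce. The design difference of 152.1 - 129.3 = 22.8 ml (SAP 8.1.1) serves below only as a yardstick.

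**2. Size in the one-vessel group**

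All inputs are assumed, since the documents give neither switching rates nor volumes by vessel number: planned one-vessel volume is lognormal with mean 130 ml and CV 0.45, and a fraction u of these patients moves to a second vessel (5% in control; 5, 10 or 15% in the device arm). Movers come evenly from the top 30% of volume, evenly from the bottom 30%, or at random. Only movement out of the group is modelled.

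- σ = √ln(1 + 0.45²) = 0.429; z at 0.70 = 0.524.
- Mover mean divided by overall mean: top 30%, r = Φ(0.429 - 0.524)/0.30 = 0.462/0.30 = 1.541; bottom 30%, r = Φ(-0.524 - 0.429)/0.30 = 0.170/0.30 = 0.567; random, r = 1.
- Mean of those who remain: 130 × (1 - u·r)/(1 - u).
- Apparent reduction with no device effect: 1 - (device mean / control mean).

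| Movers from | Control 5% | Device u | Device mean | Apparent reduction, no effect | Apparent reduction, true 15% |
|---|---|---|---|---|---|
| top 30% | 126.3 ml | 5% | 126.3 ml | 0% | 15.0% |
| top 30% | 126.3 ml | 10% | 122.2 ml | 3.3% | 17.8% |
| top 30% | 126.3 ml | 15% | 117.6 ml | 6.9% | 20.9% |
| bottom 30% | 133.0 ml | 5% | 133.0 ml | 0% | 15.0% |
| bottom 30% | 133.0 ml | 10% | 136.3 ml | -2.5% | 12.9% |
| bottom 30% | 133.0 ml | 15% | 139.9 ml | -5.2% | 10.5% |
| random | 130.0 ml | 5 to 15% | 130.0 ml | 0% | 15.0% |

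The last column is 1 - 0.85 × (device mean / control mean in the no-effect case).

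**3. Movement in both directions**

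A second calculation, also on assumed values, takes 70% planned one-vessel and 30% planned two-vessel. Mean volume in each planned-by-treated cell is the same in both arms.

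- Equal switching (0%, or 10% each way in both arms): spurious difference 0 ml in both treated-vessel groups.
- Largest positive value: cell means 130, 160, 170 and 210 ml (planned/treated 1/1, 1/2, 2/1, 2/2); upward movement 5% control and 15% device; downward 10% in both. Treated two-vessel group: control (0.035×160 + 0.27×210)/0.305 = 204.3 ml; device (0.105×160 + 0.27×210)/0.375 = 196.0 ml; difference +8.3 ml.
- Largest negative value: same means; upward 5% in both; downward 10% control and 30% device. Treated one-vessel group: control (0.665×130 + 0.03×170)/0.695 = 131.7 ml; device (0.665×130 + 0.09×170)/0.755 = 134.8 ml; difference -3.0 ml.

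Across the scenarios tried, the spurious difference was about -3.0 to +8.3 ml, against the 22.8 ml design difference. Grouping by stratum compares patients as randomised in every scenario. That comparison includes any effect of allocation that acts through the number of vessels treated.

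**The case against.** The strongest reply is that a table title is not an analysis specification. The operative text is 8.11.3.2, which names the stratification group in its heading and in its body; Protocol 7.8.2 agrees, and 9.2 announces no change. The table list is loose elsewhere: one entry is numbered 48/40, and Table 41/42 is listed for FAP and PP although 8.13 confines the roadmap-quality analysis to the device arm of PP. The title may be shorthand. This stands in part: the documents do not establish that vessels treated is the intended grouping. It does not remove the point, because the SAP elsewhere uses the same labels for vessels treated, lists the strata under another name, and offers no other output for this analysis.

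Second, losing the protection of randomisation is not the same as bias. This stands. A reader might infer that the vessel-group estimates will be biased, or biased in favour of the device. The documents do not support either: bias needs movement that differs by arm and is related to volume, and the sign depends on which patients move. If saved contrast lets low-volume cases go on to a second vessel, the one-vessel comparison is tilted against the device.

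Third, planned and treated counts may seldom differ. Elective patients already have a valid diagnostic angiogram, and ad hoc patients are randomised right after theirs. That is plausible, but the documents give no rate.

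Fourth, the analysis is exploratory. This also stands and limits the consequence.

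**Conclusion.** The inconsistency is certain: text and output name different grouping variables, and only the planned count is fixed before allocation. Whether it would bias anything is conditional. If Table 37/38 is produced as titled, the per-group tests are open to a spurious one-vessel effect of about -5% to +7% under the assumptions shown, with zero when switching is equal in both arms or unrelated to volume. Those limits rest wholly on assumed means, spread and switching rates, and are an illustration, not a forecast.

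It would be too strong to say that the trial's randomised comparison is broken. The primary and secondary tests do not use vessel number, and the sample size does not depend on it. The point is still more than editorial, because each vessel group carries its own 2.5% rejection rule and the grouping decides whether that test compares randomised patients. It should be settled before the tables are run.

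**What to change.** 1. State in SAP 8.11.3.2, in 8.13 and in the title of Table 37/38 that groups follow the vessel-number stratum recorded at randomisation, whatever was later treated.
2. Add a cross-tabulation of planned by treated vessel number in each arm, so that the extent of switching, and any difference between arms, can be seen.
3. If a version by vessels treated is also wanted, label it supplementary, note that it groups on a post-randomisation count, and record it in 9.2.

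Cost: none in patients, data collection or sample size. The EDC system needs the stratum in order to randomise, Table 3 already reports it, and vessels treated is already summarised under 8.10. The work is one grouping variable, one small table and a few lines of text.

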12 INDIVIDUAL SUBJECT DATA LISTINGS

STUDY PATIENTS		
Disposition of Patients		
Listing 1	List of Inclusion and Exclusion Criteria	
Listing 2	In- and exclusion criteria	ENROLLED
Listing 3	Randomization results	RAND
Listing 4	Visit Dates	ENROLLED
Listing 5	Study Discontinuation	ENROLLED
Listing 6	Study Completion	ENROLLED
Listing 7	Subjects Analysis Set	SCREENED
BASELINE EVALUATION		
Demographics and Baseline Values		
Listing 8	Demographics	ENROLLED
Listing 9	Medical history	ENROLLED
Listing 10	Medication	ENROLLED
PCI PROCEDURE		
Listing 11	Procedure information	SAF
Listing 12	Procedure and Fluoroscopy time	SAF
Listing 13	Procedure: Contrast Usage	SAF
Listing 14	Procedure parameters	SAF
Listing 15	Procedure: number of runs	SAF
Listing 16	End of procedure information	SAF
Listing 17	Procedural complications	SAF
Listing 18	Procedural comments	SAF
Listing 19	Treated vessel SYNTAX questions	SAF
Listing 20	Number of Vessels treated with PCI and SYNTAX score	SAF
Listing 21	Hospital Discharge	SAF
EFFICACY EVALUATION		
Analysis of efficacy		
Listing 22	Primary and Secondary Efficacy Parameters	FAP
SAFETY		

Document ID:	<As applicable, per local requirements>	Document title:	Classification:	For internal use
Modified:	11MAY2023	Statistical Analysis Plan		
Version:	3.0	Template ID:	ClinicalStudyTemplate0025	Approver:
Status:	Final	Template Version Date:	02MAR2018	Page: 45 of 52

Statistical Analysis Plan

Listing 23	Vital Signs	ENROLLED
Listing 24	Clinical Laboratory Tests	ENROLLED
Listing 25	Major Adverse Cardiovascular and Cerebral Events	ENROLLED
STUDY DEVIATIONS		
Listing 26	Study Deviations	ENROLLED

Document ID:	<As applicable, per local requirements>	Document title:	Classification:	For internal use
Modified:	11MAY2023	Statistical Analysis Plan		
Version:	3.0	Template ID:	ClinicalStudyTemplate0025	Approver:
Status:	Final	Template Version Date:	02MAR2018	Page: 46 of 52

[figure not shown]
Statistical Analysis Plan

